### 10.2. Pharmacokinetic Analysis

#### 10.2.1. Concentration Summaries

EV68-228-N serum concentrations will be listed by Dose Cohort and participant. Out-of-window sample time and PK analyses-excluded samples will be indicated, as will BQL values that were imputed for the purposes of parameter estimation ([Listing 25](#)). The listings will also indicate the nominal and actual time associated with the sample (nominal time is defined as the planned time in minutes, hours, or days since the first dose). Potentially important bioanalytical errors and their effect on the PK analysis will be discussed.

Concentrations below the quantitation limit (BQL) prior to the first measurable concentration will be imputed as zero. The first BQL concentration reported in the serum concentrations after the last measurable concentration may be imputed for the purpose of parameter estimation as the LLOQ divided by 2 only if 1) needed to estimate  $\lambda z$ , 2) all other  $\lambda z$  estimation criteria are met, and 3) if a visual predictive check of the imputed value appears to be consistent with the observed elimination trend. All other BQL samples will be treated as missing. Imputed concentration values will only be used for serum parameter estimation by NCA and not included in concentration summaries, however, imputed BQL values will be indicated by imputation method in listings with methods clarified in the footnote and denoted in figures.

EV68-228-N serum concentrations will also be summarized by Dose Cohort ([Table 77](#) and [Table 78](#)) and plotted by Dose Cohort. [Figure 12](#), [Figure 13](#), and [Figure 14](#) will present the participant serum concentration profiles using a linear plot and [Figure 15](#), [Figure 16](#), and [Figure 17](#) will present the participant serum concentration using a semilogarithmic plot. Linear plots of serum mean concentration curves will be shown in [Figure 18](#), with error bars representing  $\pm 1$  SD. Semi-logarithmic plots of geometric mean serum concentration curves will be shown in [Figure 19](#).

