## 5. SAMPLE SIZE CONSIDERATIONS

As a Phase 1, first-in-human study, the number of participants was chosen principally on feasibility and using a 5:1 randomization scheme. Thus, three cohorts of 10 participants each (n=30) and 6 placebo recipients (total N=36) are proposed. With 10 participants in each cohort receiving study product, the chance of observing at least one AE of probability 20% or more is approximately 89.3% (see [Table 3](#)). Therefore, if no AEs of a given type occur in an active dose group, we can be relatively confident that they will occur in fewer than 20% of people once the treatment is implemented.

PK parameters are not a primary outcome of the study, so it has not been powered for this, however with a sample size of 10 participants per dose level, assuming the pharmacokinetics are not dose proportional, a parameter with a coefficient of variation of 120% or less has a 90% chance to be observed within 80% and 120% of the geometric mean.

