## 10. PHARMACOKINETICS

EV68-228-N concentrations and PK parameters will be summarized by Dose Cohort. Statistics include the arithmetic mean, median, SD, geometric mean (GM), coefficient of variation (CV), minimum, and maximum. CV will be calculated using the method for log-normally distributed data and reported as a percent:

$$CV\% = \sqrt{\exp(s^2) - 1} \times 100\%, \text{ where } s^2 \text{ is the standard deviation of the log-transformed data}$$

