**Table 78: Summary Statistics of Serum EV68-228-N Concentrations by Time Point (continued)**

Dose Cohort	Sum mary Statis tics	Serum EV68-228-N Concentrations												
		Pre-Infusion (-15 min)	End of Infusion (+ 5 min)	1-hour (± 15 min)	3-hour (± 15 min)	5-hour (± 15 min)	24-hour (± 3 hr)	48-hour (± 3 hr)	7-day (± 1 day)	14-day (± 2 day)	28-day (± 3 day)	60-day (± 7 day)	90-day (± 14 day)	120-day (± 14 day)
228-N	Min, Max	XXXXXX .XXX, XXXXXX .XXX												
	Geometric Mean	XXXXXX .XXX												
	CV%	XXX												

Notes: N=Number of participants in the PK Population. Concentrations are reported in units of ng/mL.

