**Figure 18: Linear Plot of Mean ± SD of EV68-228-N Serum Concentration by Nominal Time and Dose Cohort**

[Implementation Note: Update “Units” accordingly as well as the actual LLOQ value. Samples that are <LLOQ should not be plotted]

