**Listing 25: 16.2.9.4: Participant Level Drug Concentrations**

Dose Cohort	Participant ID	Nominal Time Point (hours)	Actual Time pPoint (hours)	Sample Collected Within Time Window	EV68-228-N Concentration (ng/mL)	Used in $\lambda z$ Calculation?	Excluded from PK Analysis	Reason For Exclusion from PK Analysis
3 mg/kg EV68-228-N	XXXXXXX	Pre-Infusion	Pre-Infusion	Yes	0.00	No	No	N/A
	XXXXXXX	0	0.067	Yes	XXXX.XX	No	No	N/A
	XXXXXXX	1	1.2	Yes	XXXX.XX	No	No	N/A
	XXXXXXX	3	2.9	Yes	XXXX.XX	No	No	N/A
	XXXXXXX	5	5.5	No	XXXX.XX	No	No	N/A
	XXXXXXX	24	-	-	XXXX.XX	No	No	N/A
	XXXXXXX	48	51.25	No	XXXX.XX	No	No	N/A
	XXXXXXX	168	180.06	Yes	XXXX.XX	No	No	N/A
	XXXXXXX	336	330.25	Yes	XXXX.XX	No	No	N/A
	XXXXXXX	672	700.5	Yes	XXXX.XX	Yes	No	N/A
	XXXXXXX	1440	1442.1	Yes	XXXX.XX	Yes	No	N/A
	XXXXXXX	2160	2159.33	Yes	BQL*	Yes	No	N/A
	XXXXXXX	2880	2866	Yes	BQL	No	Yes	BQL treated as missing
10 mg/kg EV68-228-N	XXXXXXX	Pre-Infusion	Pre-Infusion	Yes	0	No	No	N/A
30 mg/kg EV68-228-N	XXXXXXX	Pre-Infusion	Pre-Infusion	Yes	0	No	No	N/A

\* Denotes a sample that was reported as BQL but was imputed as LLOQ/2 because it was necessary to compute  $\lambda z$  during the noncompartmental analysis.

Note: Missing actual time points were imputed as the nominal time point for the purpose of analysis.

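### Post-dose BQL concentrations are dropped as missing from Table 78 and Figures 18-19, so these summaries are biased upward wherever only some participants are BQL

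*SAP*

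**What the plan says.** SAP section 10.2.1 has three rules for BQL results.

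- Before the first quantifiable value: "Concentrations below the quantitation limit (BQL) prior to the first measurable concentration will be imputed as zero".
- The first BQL after the last quantifiable value may be set to LLOQ/2, but only where the terminal slope needs it.
- For the rest: "All other BQL samples will be treated as missing".

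The section then adds: "Imputed concentration values will only be used for serum parameter estimation by NCA and not included in concentration summaries". Even a value set to LLOQ/2 therefore does not reach Table 78. The shell notes to Figures 18 and 19 agree: "Samples that are <LLOQ should not be plotted".

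Section 10 lists what is summarised: "Statistics include the arithmetic mean, median, SD, geometric mean (GM), coefficient of variation (CV), minimum, and maximum". The Table 78 shell has rows for N, mean (SD), minimum and maximum, GM and CV%. It has no median row and no row for the number of BQL results. Its footnote reads "Notes: N=Number of participants in the PK Population. Concentrations are reported in units of ng/mL". Section 6.1, by contrast, asks for the non-missing sample size for every continuous variable.

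**The concern.** A BQL sample was drawn, assayed and found to be low. Treating it as missing removes only the lowest values, so the loss is never neutral. As a cohort declines through the LLOQ, the participants with the lowest concentrations leave the summary first, and the GM of those who remain stays above the LLOQ whatever the true value is. The curve then appears to flatten just above the LLOQ.

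Table 78 does not label this. Taken literally, its footnote lets N stand at the size of the PK Population while the statistics come from fewer people. Even with the non-missing n of section 6.1, a BQL result and a missed blood draw look the same.

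At stake is how the late concentrations in each cohort are described, in a study whose secondary PK objective covers about four months after infusion.

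**Working it through.** The SAP states no figure on this point, so there is none to reproduce. The check asks how far a summary of quantifiable values lies from the true value.

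**Inputs from the SAP**
- The BQL rules in section 10.2.1 and the notes to Figures 18-19.
- Cohort size from section 5: "With 10 participants in each cohort receiving study product".
- Doses of 3, 10 and 30 mg/kg.
- The only CV mentioned is 120%, in section 5.

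**Assumed, because the SAP does not give them**
- Log-normal concentrations at a given time point.
- Between-participant CV of 30%, 50% and 80%, with 120% as an outer case.
- BQL share p from 0% upward.

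**Formulas.** Let σ = √ln(1 + CV²), and let a be the standard normal quantile of p. With φ and Φ the standard normal density and distribution function:
- GM of quantifiable values / true GM = exp[σ·φ(a)/(1 − p)]
- mean of quantifiable values / true mean = Φ(σ − a)/(1 − p)
- median of quantifiable values / true median = exp[σ·Φ⁻¹((1 + p)/2)]

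**Worked case, p = 0.50.** Here a = 0 and φ(a)/(1 − p) = 0.3989/0.5 = 0.798.
- CV 30%: σ = √ln 1.09 = 0.294, so the GM ratio is exp(0.294 × 0.798) = 1.26.
- CV 80%: σ = √ln 1.64 = 0.703, so the GM ratio is exp(0.703 × 0.798) = 1.75.

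**Worked case, p = 0.20.** Here a = −0.842 and φ(a)/(1 − p) = 0.280/0.8 = 0.350.
- CV 30%: exp(0.294 × 0.350) = 1.11.
- CV 80%: exp(0.703 × 0.350) = 1.28.

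**Results (summary of quantifiable values relative to truth)**

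| BQL share | CV | GM | Mean | Median |
|---|---|---|---|---|
| 0% | any | 1.00 | 1.00 | 1.00 |
| 20% | 30% | 1.11 | 1.09 | 1.08 |
| 20% | 50% | 1.18 | 1.13 | 1.13 |
| 20% | 80% | 1.28 | 1.17 | 1.20 |
| 50% | 30% | 1.26 | 1.23 | 1.22 |
| 50% | 50% | 1.46 | 1.36 | 1.37 |
| 50% | 80% | 1.75 | 1.52 | 1.61 |

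At CV 120% the GM ratio is 1.39 at 20% BQL and 2.12 at 50%.

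**Check at the trial's size.** Simulated cohorts of 10 with CV 50% gave median GM ratios of 1.26, 1.44 and 1.70 at 30%, 50% and 70% BQL. On average 7, 5 and 3 participants were left in the summary.

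**By dose, as an illustration only.** Suppose concentrations are proportional to dose, the true GM at 3 mg/kg equals the LLOQ, and CV is 50%. The BQL shares are then 50%, 0.5% and 0% at 3, 10 and 30 mg/kg, and the GM ratios are 1.46, 1.01 and 1.00. The 30:3 GM ratio read from the table would be 10/1.46 = 6.9 instead of 10. With CV from 120% down to 30% it would be 4.8 to 7.9.

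**Simple substitution is not neutral either.** At 50% BQL and CV 50%, LLOQ/2 gives a GM of 0.85 and a mean of 0.91 times the true value. Zero gives a mean of 0.68 times the true value.

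**The case against.** The strongest reply concerns reach. The secondary PK outcome is the set of noncompartmental parameters. These come from each participant's own profile, so a rule about Table 78 does not alter them. No dose-proportionality analysis or formal comparison between doses is planned. This stands, and it sets the severity.

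Second, the information is not lost. Table 77 and Listing 25 give individual concentrations, Listing 25 marks BQL results, and with 10 active participants per cohort a reader can count them. Section 6.1 already asks for non-missing n. This largely stands, but it does not correct the printed statistics. The shell notes for the individual profile plots also leave out samples below the LLOQ.

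Third, the size is unknown. The BQL shares and CVs above are assumptions, and with no BQL through Day 121 there is no bias. This stands.

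Fourth, every simple rule is imperfect. That is true of LLOQ/2 and zero, but not of showing the BQL count or of a median taken while fewer than half are BQL.

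A reader might also infer from Listing 25, where a mock 3 mg/kg participant has BQL results at 2160 and 2880 hours with the reason "BQL treated as missing", that the sponsor expects late BQL at the lowest dose. The listing is a shell with placeholder values. It shows how such a row would be formatted and forecasts no rate.

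**Conclusion.** The rule is wrong as written, at low severity because only descriptive displays are involved. Wherever some but not all participants are BQL, the mean, GM, median and minimum in Table 78 and the mean curves in Figures 18-19 are biased upward and cannot fall below the LLOQ. The direction needs no distributional assumption.

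The size does need assumptions. It is nil with no BQL. For log-normal concentrations with CV 30-80%, the GM is inflated 1.11-1.28 fold at 20% BQL and 1.26-1.75 fold at 50%. The effect is probably largest at 3 mg/kg, provided late concentrations rise with dose and variability is similar.

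A reader might go further and conclude that half-life or clearance is biased, or that the choice of a dose for later trials is compromised. The SAP does not support this. AUC, Cmax, half-life, CL and Vz are not changed by this rule, and nothing in the SAP rests dose selection on late cohort means.

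**What to change.** In section 10.2.1 and the Table 78 shell:

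1. Show the number assayed and the number BQL at each time point. Correct the N footnote to the number of values summarised, in line with section 6.1.
2. Add the median row that section 10 promises and the shell lacks. Rank BQL results below the LLOQ, and report the median as <LLOQ when half or more are BQL.
3. Report the mean, SD, GM and CV only where the BQL share is at or below a limit that the sponsor fixes in advance. Otherwise enter NC (not calculated).
4. Report the minimum as <LLOQ whenever any value is BQL.
5. Apply the same rule to Figures 18 and 19.

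The handling of BQL in the noncompartmental analysis need not change. The cost is revised wording and a few added rows, using data already held. The downside is that some late means, most likely at the lowest dose, may become not calculated.

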### 10.2.2. Pharmacokinetic Parameters

PK analyses will be performed using noncompartmental analysis (NCA) using Phoenix WinNonlin version 8.3 or higher (Certara, Radnor, PA).

NCA PK parameters will be calculated using the actual post-dose time. Samples with concentrations greater than the LLOQ will be considered for the estimation of  $\lambda_z$ . Imputing the first BQL concentration following the last concentration greater than LLOQ to LLOQ divided by 2 will be considered on a participant-by-participant basis for participants where the  $\lambda_z$  acceptance criteria are not met by the observed data greater than the LLOQ.  $\lambda_z$  will be computed from the log-transformed concentration data. The correlation between time and concentration at the time points used to estimate  $\lambda_z$  should be sufficiently high (adjusted- $R^2 > 0.9$ ). Additionally, a minimum of three concentrations in the terminal elimination phase will be used for the calculation of  $\lambda_z$ . All concentrations used to calculate  $\lambda_z$  must come from samples taken at or after  $T_{max}$ . The concentrations used to calculate  $\lambda_z$  along with the number of concentrations used for the calculation will be included in the participant serum concentration listing ([Listing 25](#)).

The serum AUC will be computed using the linear-up log-down (linear-log) trapezoidal method.

All serum PK parameters will also be summarized by Dose Cohort using descriptive statistics ([Table 80](#)). Additionally, participant-level PK parameters will be presented by participant in [Table 79](#) in the final report.

The following parameters will be estimated:  $AUC_{0-\infty}$ ,  $AUC_{0-last}$ ,  $AUC_{0-48}$ ,  $C_{max}$ ,  $T_{max}$ ,  $t_{1/2}$ ,  $CL$ , and  $V_z$ .

See Section [3.3.4](#) for parameter definitions.

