## 2.1. Purpose of the Analyses

These analyses will assess the safety and PK of EV68-228-N after a single IV infusion in healthy adult male and female volunteers. Safety and PK data from the Phase 1 study of EV68-228-N will be used to support identification of a target dose for future efficacy trials in AFM patients.

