##### **3.1.2. Secondary**

- To characterize the PK of single ascending doses of EV68-228-N for approximately four months following the infusion.
- To measure the occurrence of Anti-Drug Antibodies (ADAs) elicited following a single IV infusion of EV68-228-N in healthy adults.

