## 4. INVESTIGATIONAL PLAN

### 4.1. Overall Study Design and Plan

This is a Phase 1, randomized, placebo-controlled, double-blinded study to assess the safety and PK of single IV administrations of EV68-228-N in healthy adult volunteers.

Three doses (3, 10 and 30 mg/kg) of EV68-228-N will be evaluated in three separate, sequential cohorts (N = 12, each cohort) in this single dose escalation study. The cohorts will be randomized in a 5:1 randomization scheme for EV68-228-N and placebo. The first two participants in each cohort will serve as sentinels. Sentinel participants may be located at different sites. Sentinel safety data will be collected through Day 3 before submitting to the Protocol Review Safety Team (PSRT) for review. The PSRT is comprised of the Principal Investigator (PI), the DMID Medical Monitor, and the DMID Medical Officer.

Data to be reviewed will include clinical data collected from Visits 1, 2 and 3, the results of laboratory testing conducted at these visits, solicited AEs and the passive reporting of AEs through Day 3. From the time of infusion of the sentinels to at least 48 hours after infusion, no new participants will be given study product or placebo, but screening may continue. If no safety signal is detected in the sentinel group, and after approval from the DMID Medical Monitor, the remaining 10 participants in the cohort will be dosed following the overall 5:1 randomization scheme.

All participants will be actively monitored for AEs and safety laboratory data following dosing through Day 8. Data will be reviewed by the PSRT and discussed with the SMC for their concurrence before advancing to the next cohort. Electronic review of the safety data by the SMC is required prior to the cohort dose escalation when halting rules are met or there are any safety concerns.

Assuming no safety concerns are identified after review of the first cohort safety data through Day 8, enrollment of Cohort 2 will begin. The dose of EV68-228-N will be increased to 10 mg/kg for the second cohort. The same sentinel design and safety plan will be used to evaluate sentinel participants in Cohort 2 and determine whether to enroll the remaining participants in Cohort 2. In addition, the same sentinel design and safety plan will be used for Cohort 3, which will evaluate the 30 mg/kg dose.

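### PK is summarised by dose cohort only; pre-specifying a descriptive dose-exposure slope with its interval would be a cheap improvement

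*SAP*

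**What the plan says.** SAP Section 2.1 states that safety and PK data from this study "will be used to support identification of a target dose for future efficacy trials in AFM patients". The secondary PK objective in Section 3.1.2 is "To characterize the PK of single ascending doses of EV68-228-N for approximately four months following the infusion". Section 4.1 gives the design: "Three doses (3, 10 and 30 mg/kg) of EV68-228-N will be evaluated in three separate, sequential cohorts".

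For the analysis, Section 10.2.2 says "All serum PK parameters will also be summarized by Dose Cohort using descriptive statistics". Section 10 lists the statistics: arithmetic mean, median, SD, geometric mean, CV, minimum and maximum. In Tables 79 and 80, AUC is in ng*h/mL and Cmax in ng/mL. No shell carries a dose-normalised AUC or Cmax, a ratio between doses, a slope, or a confidence interval for a PK parameter.

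Section 3.3.4 defines CL as dose over AUC0-∞ and Vz as CL over the terminal rate constant, so these two are dose-normalised. Section 13 has PK parameters other than AUC and Cmax printed to one decimal place, and the shells give CL in L/h.

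Dose proportionality is mentioned once, in the sample-size text of Section 5: "assuming the pharmacokinetics are not dose proportional". Section 1 says the SAP covers every planned analysis, and Section 12 (Other Analyses) is marked not applicable.

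**The concern.** A study that escalates over a tenfold dose range, and whose PK results are to inform a target dose, would usually say how exposure changes with dose and how precisely that is known. Here the reader gets three separate blocks of descriptive statistics. The SAP plans intervals elsewhere: for ADA titres and proportions, for adverse event proportions, and for differences from placebo in solicited events. It plans none for PK.

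If a statement about dose and exposure is wanted later, the model, the parameters and the handling of excluded values would be chosen after the data are seen. The size of departure at issue is not trivial. If exposure varies as dose to the power b, the dose-normalised 30:3 mg/kg ratio is 10^(b−1): 0.63 for b = 0.8, 1.00 for b = 1 and 1.58 for b = 1.2.

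**Working it through.** **The plan's own PK figure.** The SAP has no figure for a cross-dose estimate. Its only PK precision statement, in Section 5 for n = 10, is that "a parameter with a coefficient of variation of 120% or less has a 90% chance to be observed within 80% and 120" per cent of the geometric mean. On a log-normal model:

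- σ = √ln(1 + 1.2²) = 0.944
- SE = 0.944/√10 = 0.299
- P(ln 0.8 < error < ln 1.2) = 0.50, not 0.90

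A 90% chance would need a CV of about 40% or less. That is a separate matter and nothing below depends on it. The 120% is used here only as the widest CV that the SAP names.

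**Inputs.** Doses of 3, 10 and 30 mg/kg (Section 4.1). Ten active participants per dose: "three cohorts of 10 participants each (n=30) and 6 placebo recipients (total N=36) are proposed" (Section 5). The SAP gives no expected CV for a cross-dose analysis, so CVs of 20%, 30% and 40% are assumptions.

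**Model.** ln(parameter) = a + b·ln(dose).

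- ln(dose) = 1.099, 2.303, 3.401; mean 2.268
- Sxx = 10 × [(−1.169)² + 0.035² + 1.134²] = 26.53; √Sxx = 5.151
- σ = √ln(1 + CV²); SE(b) = σ/5.151
- 90% CI half-width h = 1.701 × SE(b), with t on 28 df
- factor on the dose-normalised 30:3 ratio = 10^h

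| CV | σ | SE(b) | h | factor either way |
|---|---|---|---|---|
| 20% | 0.198 | 0.0385 | 0.065 | 1.16 |
| 30% | 0.294 | 0.0570 | 0.097 | 1.25 |
| 40% | 0.385 | 0.0748 | 0.127 | 1.34 |
| 120% | 0.944 | 0.1834 | 0.312 | 2.05 |

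These assume that all 10 participants per dose contribute. AUC0-∞ could have fewer, because it needs an acceptable terminal slope.

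**Could the data support a formal claim?** An 80–125% range over a tenfold dose span corresponds to b between 1 − ln 1.25/ln 10 = 0.903 and 1.097. If b is truly 1, the chance that the whole 90% CI falls inside is 90% at CV 15%, 59% at 20%, 27% at 25%, 8% at 30% and about zero from 40%. The planned sample can give an estimate, but a formal conclusion is likely only at a CV of about 15% or less.

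**Is CL by cohort enough?** Flat CL across cohorts is the descriptive sign of proportional AUC0-∞. At one decimal in L/h, though, any CL below 0.05 prints as 0.0. Since CL = ln 2 × Vz/t½, an assumed Vz of 3 to 8 L puts CL below 0.05 once the half-life exceeds 0.693 × 3/(0.05 × 24) = 1.7 days to 0.693 × 8/(0.05 × 24) = 4.6 days. The SAP gives neither the volume nor the half-life, so this is a possibility and not a prediction.

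**The case against.** The strongest answer is that nothing promised is left undone. The objective is to describe PK at each dose, every parameter in the endpoint list is delivered, and proportionality is neither an objective nor an endpoint. Section 2.1 describes a later use of the data and sets no estimand for this SAP. PK is not powered, and the plan is descriptive throughout. All of this stands, and it is why the point is an improvement.

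Three stronger readings are tempting, and the document does not support them.

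- A reader might infer that nothing in the PK output is dose-normalised. CL and Vz are, by definition.
- A reader might infer that the study cannot say how exposure scales with dose. Table 79 gives each participant's parameters, and Table 80 gives N, geometric mean and CV% per cohort, so a slope and interval can be computed afterwards. No data are lost.
- A reader might take the phrase in Section 5 as a hypothesis left unexamined. In context it most naturally means that each dose level stands alone at n = 10, without pooling, which agrees with reporting by cohort.

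The CL argument answers only part of the point. CL has no planned interval, is in L/h while dosing is per kg, says nothing about Cmax or AUC0-48, and may be rounded too coarsely to compare cohorts.

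**Conclusion.** The point holds as a low-cost improvement. The SAP plans no cross-dose estimate or interval for any PK parameter and leaves AUC and Cmax without dose normalisation, while naming target-dose identification as a use of the data. That such work benefits from a dose-exposure slope is a reasonable inference from Sections 2.1 and 3.1.2; the SAP does not state it as a requirement.

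The achievable precision depends on a CV that the SAP does not give: about 1.25-fold either way around the estimated dose-normalised 30:3 ratio at 30%, and about 2.05-fold at 120%. A reader might take the 1.25 at CV 30% as showing that the trial would confine any departure to 0.80–1.25. That would need an estimated slope of exactly 1; the chance of the interval lying inside that range is only 8%. The case is for pre-specified estimation and not for a test.

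**What to change.** In Section 10.2.2, pre-specify a descriptive power model, ln(parameter) = a + b·ln(nominal dose in mg/kg), over the PK population for Cmax, AUC0-48 and AUC0-∞. Report b with a 90% CI, stated to be estimation only with no pass/fail criterion. Treat AUC0-last as supportive, because it stops at the last quantifiable sample and may be cut off earlier at lower doses, which would mix truncation with dose.

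Add dose-normalised Cmax and AUC columns to Table 80. Amend Section 13 and the shells for Tables 79 and 80 so that CL is printed with enough significant figures to compare cohorts.

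The cost is one small regression table and a few derived columns from data already collected. The downside is a little more programming, and an interval that may be wide and would not support a formal proportionality conclusion.
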